8.1.2. Analysis of Continuous Data

Unless specified otherwise, continuous variables will be summarised using descriptive statistics (n, mean, standard deviation (SD), median, min, max).

The change from baseline in EQ-5D ([Section 6.1.2.7](#)), FACIT-Fatigue Scale ([Section 6.1.2.8](#)), WPAI ([Section 6.1.2.10](#)) at each time point will be analyzed using mixed models for repeated measures (MMRM), with time-point as a fixed effect; the baseline value will be entered in the model as a covariate, alongside the baseline by time-point interaction. Any missing observations will be set to missing and the MMRM model will assume data are missing at random. Subjects will be fitted as a random effect where an unstructured covariance structure will be used to model the within-subject errors. The Kenward-Roger

approximation will be used to estimate denominator degrees of freedom. If the model fails to converge autoregressive 1 will be fitted instead.

The SAS procedure PROC MIXED will be used to perform the MMRM analysis.

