6.1.2.8. Change from Baseline in FACIT-fatigue

The FACIT-Fatigue score (V4.0 16Nov2007) is derived by taking the sum of the scores for the 13 questions in the instrument, resulting in a score between 0 and 52. The questions consider the patients functionality over the 7 days prior to completing the questionnaire. Higher scores represent better patient status (less fatigue).

For some of the questions, the scale indicates a higher score is better and for others, a lower score is better. Therefore, in order to ensure that higher scores represent better status, the items marked with a ‘-’ in table 4 below will be reversed by subtracting the response from “4” before summing all subscale items to derive the FACIT-Fatigue score. **Table 4. FACIT-Fatigue**

Item No.	Question	+/-
HI7	I feel fatigued	-
HI12	I feel weak all over	-
An1	I feel listless (“washed-out”)	-
An2	I feel tired	-

PFIZER CONFIDENTIAL

An3	I have trouble starting things because I am tired	-
An4	I have trouble finishing things because I am tired	-
An5	I have energy	+
An7	I am able to do my usual activities	+
An8	I need to sleep during the day	-
An12	I am too tired to eat	-
An14	I need help doing my usual activities	-
An15	I am frustrated by being too tired to do the things I want to do	-
An 16	I have to limit my social activity because I am tired	-

See [Section 7.1.3](#) for details on the rules for deriving the FACIT-Fatigue score if there is missing data.

The FACIT-Fatigue score will be derived at each time point (Baseline, Month 3, 6 and 12) and the change from baseline calculated for Month 3, 6 and 12.

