11. APPENDICES

11.1. APPENDIX 1: DATA DERIVATION DETAILS

A1.1 Definition and use of visit windows in reporting

Visit windows will be used for efficacy variables, and for any safety displays that display by month.

Visit Label	Target Day	Definition [Day window]
Enrolment	1	Day 1 or before
Month 3	91	Day 2 to 137
Month 6	183	Day 138 to Day 274
Month 12	365	Day 275 onwards

If two or more visits fall into the same window, keep the one closest to the Target Day. If two visits are equal distance from the Target Day in absolute value, the later visit should be used.

(Safety analysis may follow Pfizer standard).

A1.2 Definitions of bDMARDs and csDMARDs

The following drug names will be used to determine whether drugs are bDMARDs or csDMARDs

List of bDMARD (Brand name should be used to be able to track biosimilars)

[figure not shown]
Humira (Adalimumab)

Cimzia (Certolizumab Pegol)
Enbrel (Etanercept)
Simponi (Golimumab)
Remicade (Infliximab)
Orencia (Abatacept)
Roactemra (Tocilizumab)
Kineret (Anakinra)
Mabthera (Rituximab)
Benepali (Etanercept)
Inflectra (Infliximab)
Other

List of csDMARD

Methotrexate
Leflunomide
Hydroxychloroquine sulfate
Sulfasalazine
Other

CCI

PFIZER CONFIDENTIAL

Final Version 1.0

28-Jan-2020

Page 36 of 36

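### The SAP's MMRM, read literally, adds a redundant random subject effect to an unstructured matrix, and its AR(1) fallback assumes equal variances and equal visit spacing (minor; secondary outcomes only)

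*SAP*

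**What the plan says.** SAP 8.1.2 analyses change from baseline in EQ-5D, FACIT-Fatigue and WPAI by MMRM. Time-point is a fixed effect, and "the baseline value will be entered in the model as a covariate, alongside the baseline by time-point interaction". Baseline is therefore not a repeated response. The responses are the three post-baseline changes; SAP 6.1.2.8, for example, has "the change from baseline calculated for Month 3, 6 and 12".

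On the covariance, SAP 8.1.2 says "Subjects will be fitted as a random effect where an unstructured covariance structure will be used to model the within-subject errors". It uses Kenward-Roger degrees of freedom, and "The SAS procedure PROC MIXED will be used to perform the MMRM analysis". It adds that "the MMRM model will assume data are missing at random". There is one contingency: "If the model fails to converge autoregressive 1 will be fitted instead". The SAP does not say whether the random subject effect stays in the model when AR(1) is used. It names no heterogeneous-variance structure, time-based structure, robust standard error or further fallback step.

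Protocol 9.7.3.4 lists the fixed effects only. SAP Appendix A1.1 sets the target days at 91, 183 and 365.

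**The concern.** Taken at its word, the covariance sentence asks for a random subject effect and an unstructured residual matrix in the same model. One of these parameters is redundant. A redundant parameter can produce a singular Hessian or stop the optimiser converging, and non-convergence is the only stated reason for moving to AR(1). The specification could thus push the analysis to a more restrictive model for a reason unrelated to the data.

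AR(1) then makes two assumptions that this schedule and these outcomes may not meet: the same variance at every visit, and a correlation that depends on visit order rather than elapsed time. These MMRMs are the only model-based analyses of the three questionnaires, and SAP 7 and 8.2.5 also rely on them to handle missing data. A poor covariance model would show mainly in the standard errors and confidence intervals of the by-visit changes.

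**Working it through.** The plan gives no figure for the MMRM. Its only design figure, N = 10k/p = 10 × 10 / 0.50 = 200 (Protocol 9.5), belongs to the logistic regression. It reproduces and is not affected.

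**1. Parameter count.** With 3 responses, the covariance matrix has 3 × 4 / 2 = 6 distinct elements. The literal model is V = σ_b²·J + R, where J is a matrix of ones and R is unstructured. It has 1 + 6 = 7 parameters. The Jacobian from these 7 parameters to the 6 elements of V has rank 6. Any constant can be moved from R to σ_b² without changing V. In simulated data (200 patients, about 15% missing at Month 12), the REML log-likelihood was −217.45198 at σ_b² = 0, 0.1, 0.2, 0.3 and 0.4, with R positive definite each time. The split between σ_b² and R is not identified, but V is, and so are the fixed effects.

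**2. What AR(1) imposes.** The gaps are 183 − 91 = 92 days and 365 − 183 = 182 days, a ratio of 1.98. AR(1) sets corr(3,6) = corr(6,12) and uses one variance. If the random subject effect is kept with AR(1), the model is identified (3 parameters, rank 3) but makes the same two restrictions.

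**3. Spacing error in the planned estimates.** The documents give no correlations. Assume corr = ρ^(days/92) with ρ = 0.5 to 0.8 for Months 3–6 and equal variances, and fit the closest AR(1) by Kullback-Leibler divergence. The ratio of model SE to true SE for the by-visit mean change is:
- complete data: 1.000 at all three visits;
- 15% missing at Month 12 (assumed monotone, half lost by Month 6): 0.994 to 1.005;
- 30% missing, same pattern: 0.986 to 1.009.

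**4. Equal-variance error in the planned estimates.** Assume SDs of 1, 1.15 and 1.3 at Months 3, 6 and 12, with complete data. AR(1) replaces the three variances by roughly their average: (1 + 1.3225 + 1.69)/3 = 1.3375, an SD of 1.157. The SE ratios are:
- Month 3: 1.157/1 = 1.16;
- Month 6: 1.157/1.15 = 1.01;
- Month 12: 1.157/1.3 = 0.89.

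The fitted AR(1) gives the same ratios to two decimals, apart from Month 3 at ρ = 0.8 (1.158), across ρ = 0.5 to 0.8.

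**5. Between-visit contrasts, which the SAP does not plan.** Under the assumptions of step 3 with complete data, the SE ratio is √[(1 − ρ_AR)/(1 − ρ_true)], where ρ_AR is the fitted AR(1) correlation.

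| Assumed corr(3,6) | True corr(6,12) | Fitted AR(1) ρ | SE ratio, Month 12 − 6 | SE ratio, Month 6 − 3 |
|---|---|---|---|---|
| 0.5 | 0.254 | 0.377 | 0.914 | 1.116 |
| 0.7 | 0.494 | 0.597 | 0.892 | 1.159 |
| 0.8 | 0.643 | 0.722 | 0.883 | 1.180 |

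The first contrast is 9–12% too precise, and the second is 12–18% too imprecise.

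**The case against.** The best defence is that the sentence is loose wording. It applies the unstructured matrix to the within-subject errors, calls the model an MMRM and names PROC MIXED. All of this fits a REPEATED statement with SUBJECT= and TYPE=UN and no RANDOM statement. Protocol 9.7.3.4 mentions no random effect. This may well be what was meant, but no other part of the SAP says so, and a programmer following the text would add a RANDOM statement.

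A reader might infer that the model cannot be fitted at all. The documents do not support that. Only the split between subject variance and residual matrix is unidentified. A fit that converges, for instance with the subject variance at zero, gives the same fixed effects as the ordinary unstructured MMRM. Failure in PROC MIXED is a risk and has not been demonstrated here.

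A reader might also take the 9–18% errors in the table as errors in the reported results. They are not. The planned quantity is the change from baseline at each visit, no between-visit comparison is specified, and SAP 4 states that there are no formal hypotheses. For the planned estimates, the defence is right that unequal spacing hardly matters. It does not answer the equal-variance assumption, which acts directly on the by-visit standard errors.

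**Conclusion.** The point holds as a minor specification defect. Read literally, the SAP's first model carries one redundant covariance parameter (7 for 6 elements). This leaves the estimates identified but could set off the fallback needlessly.

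If AR(1) is used, the weakness that matters for the planned by-visit changes is its single variance: about +16% in the Month 3 SE and −11% in the Month 12 SE for assumed SDs of 1 : 1.15 : 1.3. These SDs are an illustration, since the documents give none. The spacing error alone is 0% with complete data and at most about 1.4% with 30% missing at Month 12. The larger contrast errors (9–12% too small, 12–18% too large) need three conditions together: the fallback is used, between-visit contrasts are reported, and correlation decays with time from an assumed Month 3–6 value of 0.5 to 0.8.

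Only secondary outcomes are touched (EQ-5D, FACIT-Fatigue, WPAI), in a study with no treatment comparison. SAP 8.2.3.2 also summarises them descriptively at each visit.

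**What to change.** In SAP 8.1.2, replace the random-effect sentence: the model is fitted with a REPEATED statement, SUBJECT= patient and TYPE=UN, and no RANDOM subject effect.

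Replace plain AR(1) by a fallback that has visit-specific variances and does not tie corr(3,6) to corr(6,12). One example is a spatial-power correlation on the target days with heterogeneous variances. First-order ante-dependence is another: 3 variances and 2 adjacent correlations, 5 parameters in all.

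Two common choices each mend only half of the problem. SP(POW) respects spacing but keeps equal variances. Heterogeneous Toeplitz frees the variances but still sets corr(3,6) = corr(6,12). If either is preferred for simplicity, pair it with empirical (sandwich) standard errors. The cost of that option is that sandwich standard errors cannot be combined with the Kenward-Roger method that the SAP names, so another degrees-of-freedom rule would have to be stated.

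The change is a few sentences in the SAP and about one line of SAS. It affects neither data collection, nor study size, nor the primary analysis.

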8.1.3. Analysis of Categorical Data

Unless specified otherwise, categorical variables will be summarised using counts and percentages. Percentages will be based on the number of patients with non-missing data at each visit.

8.1.4. Analysis of Binary Data

Unless specified otherwise, binary variables will be summarised using counts and percentages. Percentages will be based on the number of patients with non-missing data at each visit.

8.2. Statistical Analyses

Statistical Analysis Software, SAS (Version 9.1 or above) will be used for all analyses.

8.2.1. BACKGROUND AND DEMOGRAPHIC CHARACTERISTICS AND STUDY DISPOSITION

The Demographic and baseline variables will be summarised:

Continuous: Mean, SD, median, minimum and maximum

Categorical: Frequency and Percentage of population.

This will include age, sex, height, weight, smoking history, smoking status, educational level, social status, severity of disease, medical history (including RA diagnosis, RF and ACPA, presence of erosions on x-rays, presence of extra-articular manifestations [anemia, RA nodules, RA related vasculitis, amyloidosis or other]), vaccination status, hepatitis and tuberculosis status, comorbidities, co-medication and concomitant medication.

The number and percentage of patients at each time point will be provided along with reasons for withdrawal from the study. For patients who have discontinued Tofacitinib treatment but remain in the study information on the treatments prescribed following study treatment (Tofacitinib) will be listed.

These summaries will be based on the Full Analysis Set.

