9.4.13. Treatment of Rheumatoid Arthritis (RA-Treatment) with Tofacitinib and/or Other DMARDs

At each visit dose and route of administration (if applicable) of treatment with Tofacitinib and/or other DMARDs will be documented. In addition, stop date of previous DMARD(s), start date of new DMARD(s) and reason for switch (lack of efficacy or intolerance) will be documented.

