9.4.30. Safety Criteria

In contrast to the usual procedure for clinical trials in observational trials the treatment decision is independent of the protocol. Additionally selection criteria of patients at baseline are not as strict as for clinical trials. Thus, this study can provide new insights into the safety of Tofacitinib in routine care. All adverse events (AEs) that will occur during the observation period will be documented. Additionally, at the end of the observation both, the physician and the patient will be asked the general tolerability of the treatment with tofacitinib and reasons for premature discontinuation rates will be analysed.

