9.7.2. Safety Analysis

Adverse events will be reviewed and summarized on an ongoing basis during the study to evaluate the safety of subjects. Safety data will be presented in tabular and/or graphical format and summarized descriptively, where appropriate.

Medical history and physical examination information collected during the course of the study will not be captured for inclusion into the study database, unless otherwise noted. However, any untoward findings identified on physical examinations conducted after the administration of the first dose of study medication will be captured as an adverse event, if those findings meet the definition of an adverse event. Data collected at Screening that is used for inclusion/exclusion criteria, such as laboratory data, ECGs and vital signs will be considered source data, and will not be captured for inclusion into the study database, unless otherwise noted. Demographic data collected at Screening will be included in the study database.

Adverse events will be reported according to the 3-tier approach.

Reasons given for premature discontinuation will also be summarized.

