1. AMENDMENTS FROM PREVIOUS VERSION(S)

This is the first version of the statistical analysis plan (SAP). There are no changes to the analyses specified in the protocol.

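### The SAP specifies reasons for leaving the study, on the Full Analysis Set, but no summary of reasons for stopping tofacitinib, so the protocol's discontinuation summary is not assured

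*SAP*

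**What the plan says.** **Protocol.** Section 9.7.2 (Safety Analysis) states: "Reasons given for premature discontinuation will also be summarized". Section 9.4.30 (Safety Criteria) says that "reasons for premature discontinuation rates will be analysed". The same sentence promises that "at the end of the observation both, the physician and the patient will be asked the general tolerability of the treatment with tofacitinib". Section 9.7.1 assigns all safety analysis to the Safety Analysis Set, which needs only one dose. Sections 9.2 and 9.4.2.4 keep a patient under observation after a treatment change or after tofacitinib is withdrawn. On data collection, 9.4.1 has tofacitinib changes and their reasons recorded throughout, and 9.4.13 adds that the "reason for switch (lack of efficacy or intolerance) will be documented".

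**SAP.** Section 8.2.1 specifies: "The number and percentage of patients at each time point will be provided along with reasons for withdrawal from the study". It continues: "For patients who have discontinued Tofacitinib treatment but remain in the study information on the treatments prescribed following study treatment (Tofacitinib) will be listed". It then fixes the analysis set: "These summaries will be based on the Full Analysis Set". Under SAP 5.1 that set requires both a dose and at least one post-baseline measurement set. Sections 6.2 and 8.2.2 add treatment patterns, time on tofacitinib and time to first treatment change on the Safety Analysis Set. SAP 1 says: "There are no changes to the analyses specified in the protocol".

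**The concern.** In many trials, stopping the drug and leaving the study nearly coincide, and one disposition table serves for both. Here they are separate events by design. A patient who stops tofacitinib because of an adverse event and attends through Month 12 has discontinued the drug but has not withdrawn from the study. A table of withdrawal reasons therefore misses that patient's reason for stopping.

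The choice of analysis set affects a second group. A treated patient who leaves, or dies, before any post-baseline measurement is outside the Full Analysis Set, and so outside the table meant to show why patients left.

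This is a one-arm study in routine care, and Protocol 9.4.30 presents it as a source of new safety information. How many patients stopped for an adverse event, as distinct from lack of efficacy, is one of its main safety readings. The SAP should say how that number is produced.

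**Working it through.** No stated figure needs to be reproduced. The check compares the protocol's commitment with each SAP output that might meet it.

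| SAP output | Analysis set | Covers patients who stop tofacitinib but stay? | Gives a reason for stopping? |
|---|---|---|---|
| Study withdrawal (8.2.1) | Full Analysis Set | No | Only the reason for leaving the study |
| Later treatments after tofacitinib (8.2.1) | Full Analysis Set | Yes, as a listing | No |
| Treatment patterns (6.2, 8.2.2) | Safety Analysis Set | Largely | No |
| Time on tofacitinib, time to first change (6.2, 8.2.2) | Safety Analysis Set | Yes | No |
| Adverse event tables and listings (8.2.2) | Safety Analysis Set | Yes | None specified by reason for stopping |

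No row gives reasons for stopping tofacitinib. The patterns are also not a full count of stops. The category for moving from monotherapy to other treatment requires a switch to another DMARD. A monotherapy patient who stops and starts nothing fits none of the six categories as described.

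**Analysis set.** The Safety Analysis Set needs one dose. The Full Analysis Set needs one dose and a post-baseline measurement set. The difference is therefore exactly the treated patients with no post-baseline set, which includes the earliest losses.

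**Illustration, on assumed counts that are not in the documents.** Take 200 treated patients, the planned study size. Let:

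- w = 10 stop for an adverse event after a post-baseline visit and leave the study;
- l = 0 to 20 stop for an adverse event but stay;
- e = 0 to 20 stop for an adverse event and leave before any post-baseline set.

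Share stopping for an adverse event = (w + l + e) / 200. Share shown by the SAP 8.2.1 table = w / (200 − e).

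| l | e | Share stopping | SAP 8.2.1 table |
|---|---|---|---|
| 0 | 0 | 10/200 = 5.0% | 10/200 = 5.0% |
| 20 | 0 | 30/200 = 15.0% | 10/200 = 5.0% |
| 0 | 20 | 30/200 = 15.0% | 10/180 = 5.6% |
| 20 | 20 | 50/200 = 25.0% | 10/180 = 5.6% |

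Over this range the share stopping runs from 5.0% to 25.0%, while the specified table stays between 5.0% and 5.6%. The illustration shows only that the one table cannot stand in for the other. It does not estimate what will happen in this study.

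**Tolerability rating.** The rating in Protocol 9.4.30 is absent from the visit lists (9.4.2.1 to 9.4.2.3), from both schedules of activities (Protocol Table 5, SAP Table 1) and from every SAP endpoint and analysis. Tolerability has a row in the Protocol 9.3 variables table, but that row leaves the definition to the SAP, which gives none.

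**The case against.** A reader might infer that the study will not report how many patients stopped for adverse events. The documents do not support that. SAP 6.2 and 8.2.2 defer safety reporting to sponsor standards, and SAP 9 puts the table list in a separate document. Neither is available here, and either may contain the table. The commitment in Protocol 9.7.2 also still stands, and the SAP's statement that nothing has changed can be read as keeping it in force. This objection holds, and it limits the point to what the SAP itself specifies. It does not remove the point: Protocol 9.7 makes the SAP the place for detailed methods, and a general reference to standards does not say how to treat patients who stop the drug but remain.

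A reader might also infer that the reported safety picture will look favourable. That does not follow either. Pattern counts, time on tofacitinib and adverse events, including fatal ones, are all on the Safety Analysis Set. A patient lost early is missing from the disposition table, not from the safety results. Most drug stops will be visible; what is unspecified is their reasons.

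Neither protocol sentence on premature discontinuation names the drug. Protocol 9.1 and SAP 2.1 list discontinuation among the events that end follow-up, which fits a reading as study withdrawal. The drug-stopping reading is an inference, but a strong one: both sentences sit in safety sections, one is tied to tofacitinib tolerability, and 9.2 and 9.4.2.4 expressly continue follow-up after treatment stops. The follow-up passages need to be reconciled in any case.

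Finally, Protocol 9.5 expects drop-outs to be minimal. If so, few patients would be lost before a post-baseline visit. That says nothing about how many stop the drug and stay.

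**Conclusion.** The point holds as a gap in specification. The SAP gives reasons only for study withdrawal, on a set that excludes treated patients with no post-baseline measurements. It specifies no summary of reasons for stopping tofacitinib. A count of stops for adverse events is therefore not assured, though it may yet appear through the sponsor's standards or the separate table list.

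The size cannot be given, because the documents contain neither a rate of stopping tofacitinib nor a rate of loss before the first post-baseline visit. The conclusion rests on reading premature discontinuation as stopping the drug. The analysis-set point does not depend on that reading. The primary analysis is not affected.

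The unscheduled tolerability rating is a separate and smaller inconsistency. A general rating would not supply a count of stops for adverse events, so its absence does not cause the gap above.

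**What to change.** 1. In SAP 8.2.1, run disposition and study-withdrawal reasons on the Safety Analysis Set.
2. In SAP 8.2.2, add a Safety Analysis Set summary of reasons for permanent tofacitinib discontinuation. Keep it separate from study withdrawal and include a count due to adverse events. Use the reasons for change already recorded under Protocol 9.4.1, after confirming that a stop without a switch is recorded as a change with a reason.
3. State in the protocol or SAP that premature discontinuation means stopping tofacitinib, if that is intended, and reconcile Protocol 9.1 and SAP 2.1 with Protocol 9.2 and 9.4.2.4 on follow-up after discontinuation.
4. Separately, either add the tolerability rating to the Visit 4 list (Protocol 9.4.2.3), both schedules of activities and the SAP, or remove it from Protocol 9.4.30 and align the 9.3 row.

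The cost is SAP wording, a change of analysis set for one table, and one added table. If the tolerability rating is kept, it adds one item each for physician and patient at Visit 4. If the sponsor's standards or the table list already contain the discontinuation table, a cross-reference naming it and its analysis set would be enough for item 2.
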